## 8.8 Sub-Group Analysis

A sub-group analysis will be completed for the primary safety and primary efficacy endpoints. This analysis is not powered and is strictly for information purposes. The sub-groups are:

- Sex (females vs. males)
- Artery treated (iliac vs. femoropopliteal)

The same analysis outlined above for the primary safety and efficacy endpoints will be completed within each sub-group separately (e.g. separately for males and females).

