### 8.4 Analyses of Safety Endpoints

#### 8.4.1 Primary Safety Endpoint Analysis

The primary safety endpoint is the occurrence rate of device or procedure-related complications associated with transradial artery access through the time of hospital discharge.

The safety hypothesis being tested is:

$H_0: \pi \geq 0.07$

Vs

$H_a: \pi < 0.07$

where  $\pi$  is the proportion of subjects experiencing a radial access related complication.

A one-sided upper exact 95% CI for device or procedure-related radial artery complications rate will be calculated using the Clopper-Pearson method. The upper bound will be compared to the performance goal of 7%. If the upper bound is less than the performance goal, then this endpoint will have been successfully achieved.

Even though some subjects may contribute bilateral lesions, the safety analysis will be analyzed on a per subject basis.

The same analysis will be completed on the per-protocol analysis population if that population is different from the ITT population.

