## 12 PLANNED TESTS AND EXPECTED RESULTS

Planned a priori analyses and expected results, where applicable, are shown in Table 1.

Variable	Analysis	Expected Result	Cohort			
			ITT	PP	Non-Roll-in	Roll-in
Technical Success (Primary) Non-Roll-in Subjects Only	One-Sided Lower Exact 95% CI	Confidence Interval does not include 93%	X		X	
Technical Success (Primary) Roll-in Subjects Only	One-Sided Lower Exact 95% CI	Exploratory	X			X
Technical Success (Primary) Non-Roll-in, Per Protocol Subjects Only	One-Sided Lower Exact 95% CI	Confidence Interval does not include 93%		X	X	
Sensitivity Analysis for Primary Technical Success. Non Roll-in Subjects Only	One-Sided Lower Exact 95% CI	N/A	X		X	
Subgroup analysis for Primary Efficacy Variables by Gender and Lesion Type (Iliac and Femoral/Popliteal)	One-sided Lower Exact 95% Confidence Interval	Confidence Interval Does Not Include 93%			X	X
Major Radial Access Site Complications Attributed to Device or Procedure Through Discharge (Primary) Non-Roll-in Subjects Only	One-Sided Lower Exact 95% CI, w/wo	Confidence Interval Does Not Include 7%	X		X	

Major Radial Access Site Complications Attributed to Device or Procedure Through Discharge (Primary) Roll-in Subjects Only	One-Sided Lower Exact 95% CI	Confidence Interval Does Not Include 7%		X	X	
Major Radial Access Site Complications Attributed to Device or Procedure Through Discharge (Primary) Roll-in Subjects Only	One-Sided Lower Exact 95% CI	Exploratory	X			X
Sensitivity Analysis for Major Radial Access Site Complications Attributed to Device or Procedure Through Discharge (Primary) Non-Roll-in Subjects Only	One-Sided Lower Exact 95% CI, w/wo	N/A	X		X	
Subgroup Analysis for Major Radial Access Site Complications Attributed to Device or Procedure Through Discharge (Primary) by Gender and Lesion Type (Iliac and Femoral/Popliteal)	One-Sided Lower Exact 95% Confidence Interval	Confidence Interval Does Not Include 7%			X	X
Rate of Brite Tip Radianz Guiding Sheath Deficiencies Non-Roll-in Subjects	Two-sided Exact 95% Confidence Interval (one or more per procedure, w/wo)	Exploratory			X	
Rate of Brite Tip Radianz Guiding Sheath Deficiencies Roll-in Subjects	Two-sided Exact 95% Confidence Interval (one or more per procedure, w/wo)	Exploratory				X
Rate of SaberX Radianz PTA Balloon Catheter Deficiencies Non Roll-in Subjects Only	Two-sided Exact 95% Confidence Interval (one or more per procedure, w/wo)	Exploratory			X	

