Rate of SaberX Radianz PTA Balloon Catheter Deficiencies Roll-in Subjects Only	Two-sided Exact 95% Confidence Interval (one or more per procedure, w/wo)	Exploratory				X
Rate of S.M.A.R.T Radianz Vascular Stent System Deficiencies Non-Roll-in Subjects	Two-sided Exact 95% Confidence Interval (one or more per procedure, w/wo)	Exploratory			X	
Rate of S.M.A.R.T Radianz Vascular Stent System Deficiencies Roll-in Subjects Only	Two-sided Exact 95% Confidence Interval (one or more per procedure, w/wo)	Exploratory				X
Subgroup analysis for Secondary Safety Variables by Gender and Lesion Type (Iliac and Femoral/Popliteal)	Two-sided Exact 95% Confidence Interval (one or more per procedure, w/wo)	Exploratory			X	X
Rate of AEs; Run Separately for Non-Roll-in and Roll-in Subjects	Two-sided Exact 95% Confidence Interval (one or more per procedure)	Exploratory			X	X
Rate of Death	Two-sided Exact 95% Confidence Interval (one or more per procedure)	Exploratory			X	X
Rate of Index Limb Amputation	Two-sided Exact 95% Confidence Interval (one or more per procedure)	Exploratory			X	X
Rate of Target Lesion Revascularization	Two-sided Exact 95% Confidence Interval (one or more per procedure)	Exploratory			X	X
Rate of Procedural Complications, Separately for Non-Roll-in and Roll-in Cohorts	Two-sided Exact 95% Confidence Interval (one or more per procedure)	Exploratory			X	X
Additional Variables						
Fluoroscopy Time	Mean, 95% CI	Exploratory			X	X
Procedure Time	Mean, 95% CI	Exploratory			X	X
Time to Hospital Discharge, Minutes	Mean, 95% CI	Exploratory			X	X

Time to Hospital Discharge Eligibility, Minutes	Mean, 95% CI	Exploratory			X	X
Method of Transradial Artery Access Site Closure	Tabulation with Percentages	Exploratory			X	X
SF-36 Subscale Results	Mean, Standard Deviation and 95% CI for Each Domain	Exploratory			X	X
EQ-5D Subscale Results	Tabulations by Dimensions with Percentages for Each Domain	Exploratory			X	X
Descriptive Statistics-Age/Gender/Lesion Type (Mean, SD, Median, Min and Max or Tabulation for Categorical Variables)	Run Poolability Analysis Separately by Site	Exploratory			X	X

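### SAP Table 1 contradicts the SAP text in its primary-endpoint rows: all five safety rows name the lower bound, and the information-only subgroup rows carry the 93%/7% expected result

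*SAP*

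**What the plan says.** **Safety bound.** SAP 8.4.1 states "A one-sided upper exact 95% CI for device or procedure-related radial artery complications rate will be calculated using the Clopper-Pearson method". The endpoint is met if that upper bound is below 7%, and Protocol 14.4.1 gives the same rule. In SAP Table 1 (section 12), the five rows for major radial access site complications all specify a one-sided *lower* exact 95% interval: the main analysis, the two rows titled as roll-in only, the sensitivity analysis and the subgroup analysis.

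**Subgroups.** SAP 8.8 covers sex and artery treated. It says "This analysis is not powered and is strictly for information purposes", and then "The same analysis outlined above for the primary safety and efficacy endpoints will be completed within each sub-group separately". In Table 1 the efficacy subgroup row specifies "One-sided Lower Exact 95% Confidence Interval", with an expected result that differs only in capital letters from the primary efficacy row's "Confidence Interval does not include 93" (per cent). The safety subgroup row has the expected result "Confidence Interval Does Not Include 7" (per cent), as does the main safety row. By contrast, the row "Subgroup analysis for Secondary Safety Variables by Gender and Lesion Type (Iliac and Femoral/Popliteal" is marked *Exploratory*. Protocol 14.4.2 allows a subgroup analysis by artery and attaches no goal to it.

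**Roll-ins.** SAP 3 and 8.9 limit roll-in subjects to safety. SAP 8.9 allows their primary and secondary safety endpoints to be estimated without hypothesis testing. Table 1 nevertheless has a row "Technical Success (Primary) Roll-in Subjects Only" (marked *Exploratory*) and a roll-in tick on the efficacy subgroup row. Of the two safety rows titled as roll-in only, one is *Exploratory* and ticked for roll-ins. The other carries the 7% expected result and is ticked for the per-protocol and non-roll-in cohorts.

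**The concern.** Table 1 is the summary from which outputs are likely to be programmed and against which results are likely to be read. If its safety rows were followed as labelled, the comparison would run backwards: an interval that excludes 7% would be evidence of too many complications.

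The subgroup rows raise a question of interpretation. The SAP gives one analysis two descriptions, information only in 8.8 and a stated goal result in Table 1. The table has a label for information-only analyses but does not use it here. In a trial that covers two indications, a small subgroup with no failures at all would miss the tabled result because of its size, and could look like a shortfall.

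**Working it through.** **Inputs.** One-sided alpha 0.05 (SAP 8.1); exact Clopper-Pearson bounds; goals 93% and 7%; assumed rates 98% and 2%; 129 limbs for efficacy and 129 subjects for safety, stated power 88% (SAP 5); a minimum of 30 per indication (SAP 3, and SAP 5, which states it in subjects and in arteries). No minimum is given for either sex.

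**Reproducing the plan's figure.** At n = 129 the safety rule is met with at most 4 events: the upper bound is 6.95% at 4 and 7.98% at 5. Efficacy mirrors this, with at least 125 successes and a lower bound of 93.05%. The binomial probability of at most 4 events at a true 2% is 0.882, which matches the stated 88%. The exact one-sided alpha is 0.048.

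**Safety rows as labelled.** A lower one-sided interval excludes 7% only if the lower bound is above 7%.

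| n | Largest count still including 7% | Smallest count excluding 7% |
|---|---|---|
| 129 | 14 events, lower bound 6.7% | 15 events (11.6%), lower bound 7.3% |
| 30 | 5 events, lower bound 6.8% | 6 events (20.0%), lower bound 9.1% |

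With 0 events the lower bound is 0%, so the interval includes 7%. The n = 129 line concerns the main analysis row; the n = 30 line concerns a subgroup at the floor.

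**Subgroup rows, with the correct bound for each endpoint.** With no failures, the efficacy lower bound is 0.05^(1/n) and the safety upper bound is 1 − 0.05^(1/n).

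- n = 30: 0.05^(1/30) = 0.905, so the bounds are 90.5% and 9.5%. Neither goal is reached.
- n = 41: the safety upper bound is 7.05%. n = 42: 6.88%. The tabled result is therefore first attainable at 42.
- One failure: the upper bound is 7.09% at n = 65 and 6.99% at n = 66.
- Failures allowed: none for n = 42–65, one for 66–87, two for 88–99.

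**Chance of the tabled result, per endpoint.** Assume 129 analysed, one limb and one indication per subject, the floor of 30 applied to analysed subjects, and true rates of 98%/2%. The probability for each indication is the binomial probability of no more than the allowed failures; for n = 42 it is 0.98^42 = 0.428. The joint probability is the product.

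| Split | Smaller | Larger | Both |
|---|---|---|---|
| 30/99 | 0% | 68% | 0% |
| 41/88 | 0% | 74% | 0% |
| 42/87 | 43% | 48% | 0.428 × 0.479 = 20% |
| 63/66 | 28% | 62% | 17% |
| 64/65 | 27% | 27% | 0.274 × 0.269 = 7% |

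Across splits from 30/99 to 63/66 the larger indication lies between 48% (n = 87) and 74% (n = 88). The joint maximum over all splits is the 20% at 42/87.

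**Row title and ticks.** The safety row with the 7% expected result has per-protocol and non-roll-in ticks, the same pattern as the efficacy row titled as non-roll-in, per-protocol. Its ticks and expected result agree with each other; its title does not agree with either.

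**The case against.** The strongest reply is that the column is headed as an expected result, not as a criterion. A sponsor that assumes 98% and 2% may record what it expects without making it a test, and SAP 8.8 already warns that the subgroups are unpowered. Repeating the primary calculation within subgroups is compatible with an information-only purpose, and a reader may want the goal as a benchmark by indication. This stands in part. It is why SAP 8.8 can stay as it is, and why the subgroup rows should not be called confirmatory, a word the SAP does not use. It does not explain why the table labels its other subgroup row *Exploratory* and not these two, and at 30 to 41 observations the recorded expectation cannot occur.

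A second reply is that SAP 8.4.1 and Protocol 14.4.1 both state the upper-bound rule and its success condition plainly, so the practical risk from the wrong label is low. That stands too, but it does not make the five labels right.

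Four stronger readings are tempting and are not supported:

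- *The trial's conclusion or its type I error is at risk.* Protocol 14.4.1 defines trial success by the two overall endpoints only.
- *Subgroups will be declared met or not met.* The SAP does not say so.
- *The subgroup result is unattainable in general.* Thirty is a floor, no expected split is given, and the larger indication often reaches the result under the planning assumptions.
- *Every roll-in-only primary row is exploratory, so the subgroup rows stand alone.* One safety row so titled carries the 7% result. The clean contrast is with the secondary-safety subgroup row.

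Finally, the roll-in points depend on tick positions, which should be confirmed against the printed table.

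**Conclusion.** The inconsistency is real and confined to Table 1. The bound direction is wrong in all five primary-safety rows, not just the subgroup row; as labelled, the main row would exclude 7% from 15/129 events, against the rule of 4/129 or fewer in the text. The two primary-endpoint subgroup rows state a result that does not fit an information-only analysis and that cannot occur below 42 observations. The smaller indication would show it 0–43% of the time. The larger would show it 48–74% of the time (27% at a 64/65 split), and both together at most 20%. These chances rest on the assumed 98%/2%, 129 analysed, and one limb and one indication per subject; bilateral treatment or a different analysed number would shift them. The bounds at 30 and the threshold of 42 need only the stated method and goals.

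One safety row appears to be a mistitled non-roll-in per-protocol row. The efficacy subgroup row and one technical-success row bring in roll-ins against SAP 3 and 8.9. For roll-in safety, estimation is allowed, so only the comparison with 7% conflicts.

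No stated figure is miscalculated; the 88% reproduces. This is a minor consistency correction, worth making before outputs are programmed.

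**What to change.** Edit Table 1 only:

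1. Change *Lower* to *Upper* in the five primary-safety rows, to match SAP 8.4.1.
2. Set the expected result of both primary-endpoint subgroup rows to *Exploratory*.
3. Retitle the safety row ticked for per-protocol and non-roll-in so that its title matches its ticks.
4. Remove the roll-in tick from the efficacy subgroup row, and reconcile the roll-in technical-success row with the safety-only status in SAP 3 and 8.9. Keep any roll-in safety estimate descriptive.

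SAP 8.8 need not be rewritten. At most, add one sentence saying that any comparison with 93% or 7% within a subgroup is descriptive, which keeps the benchmark for readers who want it. The cost is a few table cells: no protocol amendment, no extra subjects, and no change to sample size or power.

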## 8.9 Analysis of Roll-in Subjects

Roll-in subjects will be summarized separately using descriptive statistics (mean, standard deviation, median, minimum and maximum values for interval level data). These subjects will be evaluated for safety only. The primary and secondary safety endpoints will be estimated for these subjects, however no formal hypothesis testing will be done.

## 8.10 Protocol Deviations

Protocol deviations will be listed by category. Descriptive statistics will be used to summarize the number of times a deviation happened over the course of the trial.

## 9 STUDY SITE POOLABILITY

Study site poolability for the primary effectiveness endpoint of technical success will be tested using a Pearson Chi-square statistic. A table whose rows are the individual study sites and the two columns are technical success (yes and no) will be used for the analysis. If the p-value for the Pearson Chi-square statistic is greater than 0.15, then the study site data can be pooled for this endpoint.

Study site poolability for the primary safety endpoint will be assessed in the same fashion as the primary effectiveness endpoint, but here the columns will be the number of subjects who did or did not experience a major, CEC-adjudicated, device or procedure-related complication associated with transradial artery access. Again, if the p-value for the Pearson Chi-square statistic is greater than 0.15, then the study site data can be pooled for the safety endpoint.

## 10 INTERIM ANALYSIS

No interim analysis is planned for this study.

## 11 HANDLING OF MISSING DATA

For both primary endpoints, a sensitivity analysis will be done where missing data is imputed using a worst-case scenario. Specifically, for the efficacy endpoint (technical success), missing data will be imputed as “unsuccessful.” Likewise, missing safety data will be imputed to indicate that the subject experienced a radial access-related AE.

If after imputing the missing data with the worst-case scenario, the interpretation of the analysis changes, then each missing data point will be imputed one at a time and the analysis re-run each time in order to see how many failed data points were needed to change the interpretation.

## 12 PLANNED TESTS AND EXPECTED RESULTS

Planned a priori analyses and expected results, where applicable, are shown in Table 1.

Variable	Analysis	Expected Result	Cohort			
			ITT	PP	Non-Roll-in	Roll-in
Technical Success (Primary) Non-Roll-in Subjects Only	One-Sided Lower Exact 95% CI	Confidence Interval does not include 93%	X		X	
Technical Success (Primary) Roll-in Subjects Only	One-Sided Lower Exact 95% CI	Exploratory	X			X
Technical Success (Primary) Non-Roll-in, Per Protocol Subjects Only	One-Sided Lower Exact 95% CI	Confidence Interval does not include 93%		X	X	
Sensitivity Analysis for Primary Technical Success. Non Roll-in Subjects Only	One-Sided Lower Exact 95% CI	N/A	X		X	
Subgroup analysis for Primary Efficacy Variables by Gender and Lesion Type (Iliac and Femoral/Popliteal)	One-sided Lower Exact 95% Confidence Interval	Confidence Interval Does Not Include 93%			X	X
Major Radial Access Site Complications Attributed to Device or Procedure Through Discharge (Primary) Non-Roll-in Subjects Only	One-Sided Lower Exact 95% CI, w/wo	Confidence Interval Does Not Include 7%	X		X	

Major Radial Access Site Complications Attributed to Device or Procedure Through Discharge (Primary) Roll-in Subjects Only	One-Sided Lower Exact 95% CI	Confidence Interval Does Not Include 7%		X	X	
Major Radial Access Site Complications Attributed to Device or Procedure Through Discharge (Primary) Roll-in Subjects Only	One-Sided Lower Exact 95% CI	Exploratory	X			X
Sensitivity Analysis for Major Radial Access Site Complications Attributed to Device or Procedure Through Discharge (Primary) Non-Roll-in Subjects Only	One-Sided Lower Exact 95% CI, w/wo	N/A	X		X	
Subgroup Analysis for Major Radial Access Site Complications Attributed to Device or Procedure Through Discharge (Primary) by Gender and Lesion Type (Iliac and Femoral/Popliteal)	One-Sided Lower Exact 95% Confidence Interval	Confidence Interval Does Not Include 7%			X	X
Rate of Brite Tip Radianz Guiding Sheath Deficiencies Non-Roll-in Subjects	Two-sided Exact 95% Confidence Interval (one or more per procedure, w/wo)	Exploratory			X	
Rate of Brite Tip Radianz Guiding Sheath Deficiencies Roll-in Subjects	Two-sided Exact 95% Confidence Interval (one or more per procedure, w/wo)	Exploratory				X
Rate of SaberX Radianz PTA Balloon Catheter Deficiencies Non Roll-in Subjects Only	Two-sided Exact 95% Confidence Interval (one or more per procedure, w/wo)	Exploratory			X	

Rate of SaberX Radianz PTA Balloon Catheter Deficiencies Roll-in Subjects Only	Two-sided Exact 95% Confidence Interval (one or more per procedure, w/wo)	Exploratory				X
Rate of S.M.A.R.T Radianz Vascular Stent System Deficiencies Non-Roll-in Subjects	Two-sided Exact 95% Confidence Interval (one or more per procedure, w/wo)	Exploratory			X	
Rate of S.M.A.R.T Radianz Vascular Stent System Deficiencies Roll-in Subjects Only	Two-sided Exact 95% Confidence Interval (one or more per procedure, w/wo)	Exploratory				X
Subgroup analysis for Secondary Safety Variables by Gender and Lesion Type (Iliac and Femoral/Popliteal)	Two-sided Exact 95% Confidence Interval (one or more per procedure, w/wo)	Exploratory			X	X
Rate of AEs; Run Separately for Non-Roll-in and Roll-in Subjects	Two-sided Exact 95% Confidence Interval (one or more per procedure)	Exploratory			X	X
Rate of Death	Two-sided Exact 95% Confidence Interval (one or more per procedure)	Exploratory			X	X
Rate of Index Limb Amputation	Two-sided Exact 95% Confidence Interval (one or more per procedure)	Exploratory			X	X
Rate of Target Lesion Revascularization	Two-sided Exact 95% Confidence Interval (one or more per procedure)	Exploratory			X	X
Rate of Procedural Complications, Separately for Non-Roll-in and Roll-in Cohorts	Two-sided Exact 95% Confidence Interval (one or more per procedure)	Exploratory			X	X
Additional Variables						
Fluoroscopy Time	Mean, 95% CI	Exploratory			X	X
Procedure Time	Mean, 95% CI	Exploratory			X	X
Time to Hospital Discharge, Minutes	Mean, 95% CI	Exploratory			X	X

Time to Hospital Discharge Eligibility, Minutes	Mean, 95% CI	Exploratory			X	X
Method of Transradial Artery Access Site Closure	Tabulation with Percentages	Exploratory			X	X
SF-36 Subscale Results	Mean, Standard Deviation and 95% CI for Each Domain	Exploratory			X	X
EQ-5D Subscale Results	Tabulations by Dimensions with Percentages for Each Domain	Exploratory			X	X
Descriptive Statistics-Age/Gender/Lesion Type (Mean, SD, Median, Min and Max or Tabulation for Categorical Variables)	Run Poolability Analysis Separately by Site	Exploratory			X	X

All variables that are measured by procedure—and without—will be listed comprehensively with details. The analyses indicated as being performed on a per procedure basis will be analyzed this way to assure statistical independence, but all results will be reported. Therefore, for example, if there is more than one procedural complication in a given procedure, all complications will be listed.

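### SAP Table 1 gives a lower confidence bound in all five primary-safety rows, but the safety rule needs the upper bound

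*SAP*

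**What the plan says.** SAP 8.4.1 tests H0: π ≥ 0.07 against Ha: π < 0.07 and states the method: "A one-sided upper exact 95% CI for device or procedure-related radial artery complications rate will be calculated using the Clopper-Pearson method". The endpoint is met if that upper bound is below 7%. Protocol 14.4 (Primary Analysis, Safety) gives the same rule and makes trial success depend on meeting both primary endpoints. For the per-protocol set, 8.4.1 adds: "The same analysis will be completed on the per-protocol analysis population if that population is different from the ITT population".

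SAP 12 introduces its table with: "Planned a priori analyses and expected results, where applicable, are shown in Table 1". Five rows concern major radial access site complications:

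| Row | Bound in Table 1 | Expected result |
|---|---|---|
| Primary, ITT, non-roll-in | Lower | excludes 7% |
| Ticked PP and Non-Roll-in, labelled as roll-in only | Lower | excludes 7% |
| Roll-in | Lower | exploratory |
| Sensitivity (missing data) | Lower | N/A |
| Subgroups | Lower | excludes 7% |

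The wording "One-Sided Lower Exact 95% CI, w/wo" stands in the primary and sensitivity rows. The other three name the same bound without the suffix. The expected result in the first, second and fifth rows is "Confidence Interval Does Not Include 7" (percent).

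**The concern.** To show that a complication rate is below a goal, the upper bound must lie below that goal. A lower bound says only how small the rate could be. The technical-success rows of the same table use a lower bound correctly, because success there means exceeding 93%. The safety rows look like a copy of that wording.

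The SAP therefore gives opposite bounds for one co-primary endpoint. Outputs programmed or checked against Table 1 would print the wrong bound. In the three rows with a stated result they would contradict 8.4.1. The sensitivity row has no stated result to reverse, but SAP 11 relies on that analysis to show whether worst-case imputation changes the interpretation, and a lower bound cannot show this.

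A second slip sits in the same block. The safety row ticked PP and Non-Roll-in is labelled as roll-in only. The efficacy row with the same ticks is "Technical Success (Primary) Non-Roll-in, Per Protocol Subjects Only", so this is presumably the per-protocol safety row.

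**Working it through.** **Inputs.** One-sided α = 0.05 (SAP 8.1), goal 7% (SAP 8.4.1), assumed true rate 2% and n = 129 with 88% power (SAP 5).

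**Formulas (one-sided 95% Clopper-Pearson), x events in n subjects.**
- Upper: U(x, n) = 0.95 quantile of Beta(x + 1, n − x)
- Lower: L(x, n) = 0.05 quantile of Beta(x, n − x + 1)

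**Step 1: reproduce the plan's power.** The largest x with U(x, 129) < 7% is 4. Power is P(X ≤ 4 | 129, 0.02) = 0.882, and exact type I error is P(X ≤ 4 | 129, 0.07) = 0.048. The stated 88% is reproduced. The same rule at one-sided 0.025 gives 74.1%, and a normal approximation gives 85.5%. The design was therefore sized on the upper bound at one-sided 0.05.

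**Step 2: both bounds at n = 129.**

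| Events | Observed | Upper bound | Lower bound |
|---|---|---|---|
| 3 | 2.33% | 5.90% | 0.64% |
| 4 | 3.10% | 6.955% | 1.07% |
| 5 | 3.88% | 7.98% | 1.54% |
| 14 | 10.85% | 16.4% | 6.68% |
| 15 | 11.63% | 17.3% | 7.31% |

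**Step 3: compare the two rules.**
- SAP 8.4.1 is met with 0 to 4 events.
- Table 1 read literally uses the interval from L to 100%. It excludes 7% only if L > 7%, which first happens at 15 events.
- No count meets both rules, and 5 to 14 events meet neither.
- At a true rate of 2%, the probabilities are 0.882 for 8.4.1 and P(X ≥ 15) = 5.7 × 10⁻⁸ for the table.

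**Step 4: the opposite misuse.** If someone instead passed the device whenever L < 7%, up to 14 events would pass. The chance of passing would be 96.3% at a true rate of 7% and 69.1% at 10%.

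**Step 5: sensitivity row, with assumed counts.** Suppose worst-case imputation raises events from 3 to 5. The upper bound moves from 5.90% to 7.98%, and the conclusion is lost. The lower bound moves from 0.64% to 1.54% and stays below 7% throughout, so the loss is invisible.

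**Step 6: dependence on n.** The upper bound at 4 events is 7.17% at n = 125, 7.01% at 128, 6.955% at 129 and 6.90% at 130. The passing count is thus 3 for n = 125 to 128 and 4 for n = 129 to 131. The literal lower-bound threshold is 15 for every n from 125 to 131.

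**Step 7: subgroups.** At the planned minimum of 30 subjects per artery, U(0, 30) = 9.50%. Even no events would not put the upper bound under 7%.

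**The case against.** The strongest reply is that this is a clerical carry-over with little practical effect. SAP 8.4.1 and Protocol 14.4 state the full rule correctly, and the hypotheses and sample size agree with it. SAP 8.8 applies the primary analysis to subgroups. Table 1 lists expected results and does not set success criteria. Nobody would seriously read it as hoping for a rate above 7%, so the 15-event threshold describes an unlikely reading. This stands as a limit on severity: the realistic harm is a wrong bound in an output, and a programmer who notices will turn to 8.4.1.

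A second reply is that a one-sided lower interval could mean the interval for a lower-tailed alternative, running from 0 to U. Excluding 7% would then be correct. This does not hold up: SAP 8.4.1 calls that interval upper, and the same table uses *Lower* for the lower bound on technical success.

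Two points about the remedy are fair. Once the bound is corrected, excluding 7% is equivalent to an upper bound below 7%, so rewording the expected result adds clarity only. And the efficacy subgroup row has the same features as the safety subgroup row (a stated pass result, ticked for roll-ins), so both should be treated alike.

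**Conclusion.** The inconsistency is real. All five primary-safety rows of Table 1 name the wrong bound, and in three of them the stated expected result, read literally, is reached only when the device is shown to miss the goal. At n = 129 this sets a threshold of 15 or more events against a pass limit of 4 or fewer.

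The decision rule in SAP 8.4.1, the protocol rule, the sample size and the 88% power are untouched. This is therefore a correction to make before the analysis is programmed and run, and not a flaw in the design. The event counts assume exactly 129 analysed subjects; the direction of the error does not depend on n. The imputation example uses assumed counts. That the mislabelled row is the per-protocol row is inferred from its tick marks and the matching efficacy row.

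**What to change.** In SAP Table 1:

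1. Change *Lower* to *Upper* in all five rows for major radial access site complications.
2. In the primary and per-protocol rows, preferably state the expected result as an upper bound below 7%. Do not give a fixed event count: n is approximate (SAP 3), ITT requires an attempted device insertion (SAP 6), and 4 events pass at 129 subjects but not at 128.
3. Mark the safety subgroup row exploratory, and the matching efficacy subgroup row with it. SAP 8.8 describes these analyses as unpowered and informational, both rows are ticked for roll-ins, for whom SAP 8.9 rules out formal testing, and the secondary-safety subgroup row is already exploratory.
4. Relabel the safety row ticked PP and Non-Roll-in as per-protocol, non-roll-in, after confirming that this is what was meant.

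Correct the cells directly. Do not add a general clause that 8.4.1 prevails over Table 1. Section 8.4.1 describes the endpoint as "occurrence rate of device or procedure-related complications associated with transradial artery access through the time of hospital discharge", without the restriction to major, CEC-adjudicated events found in SAP 4.1, SAP 9 and Protocol 8.1.1. Keep *Major* in the Table 1 rows.

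The cost is a few edited table cells, with no change to the protocol, sample size or data collection.
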